**Table 13 Example: For patients who achieved a 1-category PGIS improvement from baseline at Month 6**

		Baseline PGIS			
		Mild	Moderate	Severe	Total
Percent change in modified BPI-SF3 from baseline to month 6	n				
	Mean (SD)				
	10 th Percentile (P10)				
	25 th Percentile (Q1)				
	Median				
	75 th Percentile (Q3)				
	90 th Percentile (P90)				
	Min, Max				

BPI-SF3 = Brief Pain Inventory – Short Form item 3; PGIS = Patient Global Impression of Severity.

**Table 14 Example: For patients who achieved a 2-category PGIS improvement from baseline at Month 6**

		Baseline PGIS		
		Moderate	Severe	Total
Percent change in modified BPI-SF3 from baseline to Month 6	n			
	Mean (SD)			
	10 th Percentile (P10)			
	25 th Percentile (Q1)			
	Median			
	75 th Percentile (Q3)			
	90 th Percentile (P90)			
	Min, Max			

BPI-SF3 = Brief Pain Inventory – Short Form item 3; PGIS = Patient Global Impression of Severity.

### ***15.2.5.10 Associations between change in neuropathic pain and other manifestations of FD, including plasma Gb3***

#### ***15.2.5.10.1 Abdominal pain***

The absolute change from baseline (Month 6 – baseline) in the NRS-11 score will be used to reflect the change in abdominal pain.

The analysis will be conducted on the set of subjects with a modified BPI-SF3 score available at Month 6 and non-missing change from baseline in the NRS-11 score. The analysis will be conducted on the two study treatment groups combined.

A scatter plot will represent the change from baseline in the NRS-11 score on the y-axis vs the absolute change in modified BPI-SF3 on the x-axis, and the corresponding Pearson and Spearman correlation coefficients will be provided with their 95% confidence limits.

This analysis will be implemented by the following SAS® code:

```
proc corr pearson spearman;  
  with nrs11change;  
  var percentchange;  
run;
```

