the same plot for each anchor category. The eCDF will show the cumulative proportion of subjects who reach a given modified BPI-SF3 change or more (on the y-axis) vs the change in modified BPI-SF3 (on the x-axis) and will be presented on the same plot for each anchor category. The eCDF plots will primarily be used to determine a reasonable range of meaningful change thresholds by estimating the 25th, 50th and 75th percentile change in modified BPI-SF3 among the improvement categories of the anchors.

In addition, supportive receiver operator characteristic curve analyses will be conducted using logistic regressions on the pre-specified response criteria defined by the anchor variables and the change in modified BPI-SF3 as explanatory variable.

Associations between change in neuropathic pain and other manifestations of FD

In order to show that improvement in neuropathic pain is not associated with deterioration of other manifestations of FD, an analysis of the correlation between the percent change from baseline in modified BPI-SF3 at Month 6 and endpoints related to GI symptoms will be provided graphically by means of a scatter plot displaying the coefficient of correlation.

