15.2.5.10	Change from baseline to M6	None	Descriptive	Investigates associations between change in neuropathic pain and changes in other FD manifestations (abdominal pain, diarrhea). Scatter plots by treatment group of change in modified BPI-SF3 score vs change in the considered symptom, Spearman correlation coefficients.

M1, M2, ..., M6: Month 1, 2, 3, 4, 5, 6.

ANCOVA = Analysis of covariance; BPI-SF3 = Brief Pain Inventory-Short Form item 3; CMH = Cochran-Mantel-Haenszel test; CR = Copy Reference; FAS = Full analysis set; FD = Fabry disease; MAR = Missing at random; MI = multiple imputation; MNAR = Missing not at random; MMRM = mixed model for repeated measures; NR = non-responder; PGIC = Patient Global Impression of Change; PGIC-DS = Patient Global Impression of Change in Disease Severity; PGIC-PS = Patient Global Impression of Change in neuropathic Pain Severity; PGIS-D = Patient Global Impression of Severity of Disease; PGIS-P = Patient Global Impression of Severity of neuropathic Pain; PPS = Per-protocol analysis set; ROC = receiver operating characteristic; SI = single imputation.

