#### ***15.2.5.10.3 Plasma Gb3***

The analysis described in Section [15.2.5.10.1](#) will be repeated with the change from baseline to Month 6 in plasma Gb3.

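### SAP 15.2.5.10 correlates pain change with symptom and Gb3 change across pooled arms without adjusting for arm, and its text, code and Table 12 disagree on the specification

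*SAP*

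**What the plan says.** SAP 15.2.5.10.1 (abdominal pain) sets the method: "The analysis will be conducted on the two study treatment groups combined". The scatter plot places symptom change on the y-axis against "the absolute change in modified BPI-SF3 on the x-axis, and the corresponding Pearson and Spearman correlation coefficients". The SAS code beneath it, however, has "var percentchange" as the pain variable. Section 15.2.5.10.2 (diarrhea) takes over this approach, and in 15.2.5.10.3 the analysis "will be repeated with the change from baseline to Month 6 in plasma Gb3". None of the three subsections asks for a coefficient within arm or adjusted for arm.

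The row for 15.2.5.10 in SAP Table 12 reads differently: "Scatter plots by treatment group of change in modified BPI-SF3 score vs change in the considered symptom, Spearman correlation coefficients". It names abdominal pain and diarrhea, not Gb3, and it lists no Pearson coefficient. It classes the analysis as descriptive.

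Protocol 10.3.2.5 specifies a correlation between "the percent change from baseline in modified BPI-SF3 at Month 6 and endpoints related to GI symptoms". Its stated aim is to show that pain relief does not go along with worsening elsewhere in the disease. SAP section 20, which records departures from the protocol, covers subgroups only.

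**The concern.** A correlation over both arms of a randomized trial mixes two things: how the variables move together among subjects on the same treatment, and how far apart the arms lie on each variable. If lucerastat lowers both pain and Gb3, the two arms form two displaced clouds, and the pooled coefficient is positive even if no subject's pain change is related to that subject's Gb3 change. Gb3 is where this matters most, because the protocol expects it to fall on lucerastat relative to placebo.

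For the symptom correlations the stated aim is reassurance that pain relief is not bought with deterioration. If treatment improves both variables, pooling pushes the coefficient in the reassuring direction and could hide an adverse within-arm association.

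The metric mismatch is a separate specification error. A programmer cannot satisfy both text and code, and the choice between them would be made outside the plan.

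**Working it through.** **The plan's own figure.** Protocol 10.5 gives 87.2% power for a difference of 2 points, SD 3, 66 against 33 subjects, two-sided 5%. A noncentral t calculation returns 87.20%. The standardized pain effect is therefore d1 = 2/3 = 0.667. The documents state no figure for the correlations themselves.

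**Formula.** Let p be the share on lucerastat, w the common within-arm correlation, and d1, d2 the treatment effects in within-arm SD units (equal SDs in both arms). Then

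r(pooled) = [w + p(1−p)·d1·d2] / √{[1 + p(1−p)·d1²]·[1 + p(1−p)·d2²]}

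With 2:1 allocation, p(1−p) = 2/3 × 1/3 = 2/9.

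**Pain and Gb3, w = 0.** The documents give no standardized effect for absolute Gb3 change, so d2 is an assumption, shown as a range. The top value is 55/10 = 5.5, from the Phase 1b percent change of −55% (SD 10) in protocol 1.2.3. That was measured at Week 12 on top of ERT, and the control SD is assumed equal.

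Worked case, d2 = 3: the numerator is 2/9 × 0.667 × 3 = 0.444 and the denominator is √(1.0988 × 3) = 1.816, so r = 0.245. The intervals use Fisher's z with all 118 randomized subjects (SAP section 2); at d2 = 3, atanh(0.245) ± 1.96/√115.

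| Assumed d2 | Pooled r | 95% CI, n = 118 |
|---|---|---|
| 1 | 0.13 | −0.05 to 0.30 |
| 2 | 0.21 | 0.03 to 0.37 |
| 3 | 0.25 | 0.07 to 0.41 |
| 4 | 0.27 | 0.09 to 0.43 |
| 5.5 | 0.28 | 0.10 to 0.44 |

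The ceiling at this pain effect, as d2 grows without limit, is 0.667·√(2/9)/√1.0988 = 0.30. A simulation of 5,000 trials (79 and 39 subjects, d2 = 3, w = 0) gave a mean pooled Pearson r of 0.25 and Spearman of 0.23, nominally significant Pearson tests in 78% of trials, and a mean within-lucerastat r of 0.00.

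**Dependence on the pain effect.** At half the planned effect (d1 = 1/3), pooled r is 0.07, 0.13 and 0.15 (0.145 before rounding) for d2 = 1, 3 and 5.5. With no pain effect it is 0.

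**Pain and abdominal pain, w = 0.** Protocol 10.5 gives a difference of 1.5 to 2.5 and an SD of 2.5 to 3.5. At 2 and 3, r = (2/9 × 0.444)/1.0988 = 0.09. Across the range, r runs from 0.06 (1.5, SD 3.5) to 0.13 (2.5, SD 2.5).

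**Masking.**
- w = 0.4 with Gb3, d2 = 3, no pain effect: 0.4/√3 = 0.23.
- w = −0.10 with abdominal pain, both effects 2/3: (−0.10 + 0.0988)/1.0988 = 0.00.
- w = −0.20 with Gb3, d2 = 3, d1 = 2/3: (−0.20 + 0.444)/1.816 = +0.13.

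**The pain metric, place by place.** Protocol 10.3.2.5: percent. SAP 15.2.5.10.1 text: absolute. SAP 15.2.5.10.1 code: percent. SAP Table 12: a change in score, with no statement of which kind.

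**The case against.** The case for leaving this alone has real content. The analysis is descriptive, it lies outside the fixed testing sequence, and no document says the Gb3 correlation will be offered as proof of mechanism. The neighbouring anchor analyses (SAP 15.2.5.8 and 15.2.5.9) also combine the arms, so pooling looks deliberate and Table 12 may be the stale text. The Gb3 figures rest on an assumed effect: at 1 SD the interval includes zero. The intervals assume that all 118 subjects contribute, although the section requires non-missing values on both variables. A placebo-arm coefficient from about 39 subjects would have limits of roughly ±0.32 around zero, and Phase 1b controls showed no Gb3 change, so that arm may say little.

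Most of this limits the size of the point and leaves its substance standing. The anchor analyses ask how a score change maps to a patient's global rating, which is a question about the scale. Whether pain change tracks a pharmacodynamic marker is a different question, and there treatment arm is a confounder.

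Four stronger readings are tempting, and the documents do not support them:
- *Table 12 directly contradicts the Gb3 analysis.* Its row does not mention Gb3. That conflict arises only because 15.2.5.10.3 inherits the pooled method. The words on treatment group also attach to the plots, and whether they cover the coefficients is unclear.
- *The absolute/percent mismatch helps create the spurious correlation.* Only pooling does that.
- *The code is the error and should be changed to absolute change.* The code agrees with the protocol; it is the SAP text that departs from it.
- *Type I error is inflated.* No controlled hypothesis is involved.

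**Conclusion.** The specification is wrong as written, on two separate counts, and the consequence is modest.

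First, pooling without any arm-adjusted coefficient lets a treatment effect on both variables create or mask an association. For Gb3 the artefact is about 0.13 to 0.28. This assumes the planned pain effect, 2:1 allocation, equal within-arm SDs, no within-arm correlation, and a standardized Gb3 effect between 1 and 5.5 that the documents do not fix. At 3 SD the interval is about 0.07 to 0.41 with all 118 subjects, and wider with missing data. For abdominal pain the artefact is small. The documents allow no comparable figure for diarrhea. The risk is to how the coefficients are interpreted, not to any confirmatory claim.

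Second, SAP text and code name different pain variables, the protocol sides with the code, and no change is declared.

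**What to change.** Report Pearson and Spearman coefficients within each arm, plus a partial correlation adjusted for treatment arm, at least for Gb3. State that the placebo-arm estimate, from about 39 subjects, will be imprecise; the arm-adjusted coefficient is the more useful single summary. If a pooled coefficient is kept, label it as including the between-arm difference.

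Make Table 12 and 15.2.5.10 agree on by-arm or pooled presentation, on which coefficients are reported, and on whether Gb3 is included.

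Use one pain metric in protocol, SAP text and code: percent change as in the protocol, or both. If absolute change is kept, declare it in SAP section 20.

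The cost is a BY statement, a partial-correlation run, consistent variable names, and short edits to the text, Table 12 and, if needed, section 20. While the code is open, note that it lacks the Fisher option used in 15.2.5.8, although confidence limits are promised here too. No new data are needed, and the primary and secondary analyses are unaffected.

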#### ***15.2.5.10.2 Diarrhea***

The change from (Month 6 – baseline) in the number of days with at least one stool of a BSS consistency Type 6 or 7 will be used to reflect the change in diarrhea symptoms.

The analysis will follow the same approach as in Section [15.2.5.10.1](#).

#### ***15.2.5.10.3 Plasma Gb3***

The analysis described in Section [15.2.5.10.1](#) will be repeated with the change from baseline to Month 6 in plasma Gb3.

### **15.2.6 Subgroup analyses**

The aim of these exploratory subgroup analyses, classifying subjects according to important baseline characteristics, is to explore the consistency of treatment effect in a variety of relevant subject subgroups to support the efficacy evaluation of lucerastat in this indication.

The subgroups considered in these analyses are defined in Section [6](#).

Results of the subgroup analyses will be displayed in a forest plot as described in [[Cuzick 2005](#)] and will include:

1. An estimate of the treatment effect (LS-mean difference for lucerastat vs placebo) with its 95% CI for each level of each subgroup. It will be calculated as described for the primary analysis [Section [15.2.3](#)]. The ANCOVA will also include the subgroup and the subgroup \* treatment interaction.

2. A p-value for the interaction tests obtained from the ANCOVA described above.
3. A vertical reference line displayed at the level of the overall treatment effect.

The study is not designed or powered to detect interactions but an arbitrary two-sided significance level of  $\alpha = 0.10$  will be used for the interpretation of the interaction test. No multiplicity adjustment is introduced as the subgroup analyses are exploratory in nature.

### 15.3 Analysis of the secondary efficacy variables

The hypotheses for the secondary endpoints related to abdominal pain and plasma Gb3 are defined in the same way as described for the primary endpoint in Section 15.2.1.

The null hypothesis for the secondary endpoint related to stool consistency is that both groups are from identical distributions while the alternative hypothesis is that the distributions differ with respect to location.

#### 15.3.1 Change from baseline to Month 6 in the NRS-11 score of “abdominal pain at its worst in the last 24 hours” in subjects with GI symptoms at baseline

The same approach (CR MI + ANCOVA as main analysis with MAR MI and J2R MI + ANCOVA as sensitivity analyses) as described in Sections 15.2.3 and 15.2.4 will be used to analyze this endpoint on the mFAS-GIS. Subjects with the baseline value missing will be excluded from this analysis.

Subgroup analyses will be performed similarly to those described in Section 15.2.6 by including the respective subgroup and subgroup by treatment interaction in the ANCOVA.

The following supportive analyses will be performed:

- The same approach (CMH test) as described in Section 15.2.5.1 will be used to analyze a response variable (yes/no) defined as a reduction from baseline to Month 6 of at least 50% in the NRS-11 score.
- The same approach (MMRM) as described in Section 15.2.5.5 will be used to characterize the treatment effect over time.

Patterns of missingness will be summarized as described in Section 15.2.2. An eCDF plot of the absolute change from baseline to Month 6 by treatment arms will be provided as well.

Descriptive summary statistics of the absolute values and changes from baseline will be provided on the mFAS-GIS and the mFAS.

#### 15.3.2 Change from baseline to Month 6 in the number of days with at least 1 stool of a BSS consistency Type 6 or 7 in subjects with GI symptoms at baseline

This endpoint will be analyzed using the mFAS-GIS. All available data will be used regardless of occurrence of ICEs such as premature treatment discontinuation or changes

in background medication. Subjects with a missing baseline value will be excluded from the analysis.

The change from baseline to Month 6 in the number of days with at least 1 stool of a BSS consistency Type 6 or 7 will be analyzed using a non-parametric rank analysis of covariance [Quade 1967, Koch 1982, Koch 1990, Stokes 2012] adjusted for the baseline value and stratified by sex and ERT treatment status at screening, as follows:

1. Produce standardized ranks for the baseline variable (covariate) and the change from baseline to Month 6 variable (response) within each stratum. Standardized ranks are used to adjust for the fact that the number of subjects differ among strata.
2. Fit a separate linear regression model for each stratum with the standardized ranks of the baseline variable and the change from baseline to Month 6 variable as independent and dependent variable, respectively. Retain the regression residuals.
3. Apply the stratified CMH mean score test using the residuals as scores to compare treatment groups. The p-value from this test will be used to test the null hypothesis.

The three steps will be implemented using the following SAS® code.

```
/* 1) Produce standardized ranks for covariate BASE and response variable CHG - ensure to
impute ranks for CHG as described in the text below prior to this step */
* nplus1 option requests fractional ranks by using denominator n+1 where n is the strata-
specific sample size;
* ties=mean option requests midranks;
proc rank data = input nplus1 ties = mean out = ranks;
  by sex ert_status;
  var base chg;
run;

/* 2) Linear regression for each stratum on standardized ranks; output residuals */
proc reg data = ranks noprint;
  by sex ert_status;
  model chg = base;
  output out = residual r = resid;
run;

/* 3) Stratified mean score test, using values of residuals as scores, to compare
treatment groups */
proc freq data = residual;
  tables sex*ert_status*treatment*resid / noprint cmh2;
run;
```

The rank analysis of covariance does not provide an interpretable treatment effect estimate. Therefore, the magnitude of the treatment effect will be estimated using the unadjusted

non-parametric win ratio [Wang 2016] between lucerastat and placebo with corresponding 95% CI, derived via bootstrap (100,000 samples) using the bias-corrected method [Carpenter 2000] on the log-transformed win ratio. The rejection of the null hypothesis will be solely based on the p-value from the rank analysis of covariance and not the 95% CI of the unadjusted win ratio estimator.

Bootstrapping will be implemented using the following SAS® code:

```
proc surveyselect data=ranks out=boot seed=197 method=urs samprate=1 reps=100000 outhits;  
  strata treatment;  
run;
```

Aligned with the treatment policy strategy, all subjects with a valid value for the change from baseline to Month 6 will be ranked based on these values (such that larger decreases are associated with better ranks). Subjects with a missing value for the change from baseline to Month 6 will be assigned worse ranks than subjects with available change from baseline to Month 6 values based on their last available change from baseline value prior to Month 6. Subjects with a non-missing baseline value but no post-baseline data will be assigned the worst rank. Mid-ranks are used in the event of ties.

To explore the robustness of inferences from the main analysis described above to deviations from its assumptions regarding missing data, the above analysis will be repeated as a sensitivity analysis using the following rules for ranking of subjects with missing data. As above, subjects with a missing value for the change from baseline to Month 6 will be assigned worse ranks than subjects with available change from baseline to Month 6 values, based on their last available change from baseline value prior to Month 6. However, these subjects will then be divided into four quarters using the first quartile, median and third quartile of their last available change from baseline value. Within each quarter, lucerastat subjects will be assigned worse ranks than placebo subjects. Lucerastat subjects with a non-missing baseline value but no post-baseline data will be assigned the worst rank. Placebo subjects with a non-missing baseline value but no post-baseline data will be assigned the second worst rank. Mid-ranks are used in case of ties.

The win ratio together with its 95% CI will also be derived within each subgroup defined in Section 6 (using the ranking for the main analysis described above), and presented in a forest plot. Bootstrapping will be performed separately for each subgroup to ensure constant numbers of subjects by treatment group within each bootstrap sample, using the following SAS® code:

```
proc surveyselect data=ranks out=boot seed=197 method=urs samprate=1 reps=100000 outhits;  
  strata treatment subgroup;  
run;
```

The following supportive analyses will be performed:

- The same approach (CMH test) as described in Section 15.2.5.1 will be used to analyze a response variable (yes/no) defined as a reduction from baseline to Month 6 of at least 50% in the number of days with at least one stool of a BSS consistency Type 6 or 7 in subjects who have diarrhea at baseline.
- The same approach (MMRM) as described in Section 15.2.5.5 will be used to characterize the treatment effect over time.

Patterns of missingness will be summarized as described in Section 15.2.2. An eCDF plot of the absolute change from baseline to Month 6 by treatment arms will be provided as well.

Descriptive summary statistics of the absolute values and changes from baseline will be provided on the mFAS-GIS and the mFAS.

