10.3.3.2 Change from baseline to Month 6 in the number of days with at least 1 stool of a Bristol Stool Scale consistency Type 6 or 7 in subjects with gastrointestinal symptoms at baseline

This endpoint will be analyzed using the mFAS-GIS. All available data will be used regardless of occurrence of intercurrent events such as premature treatment discontinuation or changes in background medication. Subjects with a missing baseline value will be excluded from the analysis.

The change from baseline to Month 6 in the number of days with at least 1 stool of a Bristol Stool Scale consistency Type 6 or 7 will be analyzed using a non-parametric rank analysis of covariance [Quade 1967, Koch 1982, Koch 1990, Stokes 2012] adjusted for the baseline value and stratified by sex and ERT treatment status at screening, as follows:

1. Produce standardized ranks for the baseline variable (covariate) and the change from baseline to Month 6 variable (response) within each stratum. Standardized ranks are used to adjust for the fact that the number of subjects differ among strata.
2. Fit a separate linear regression model for each stratum with the standardized ranks of the baseline variable and the change from baseline to Month 6 variable as independent and dependent variable, respectively. Retain the regression residuals.

3. Apply the stratified Cochran-Mantel-Haenszel mean score test using the residuals as scores to compare treatment groups. The p-value from this test will be used to test the null hypothesis.

An example SAS code to perform the three steps above will be provided in the SAP.

The rank analysis of covariance does not provide an interpretable treatment effect estimate. Therefore, the magnitude of the treatment effect will be estimated using the unadjusted non-parametric win ratio [Wang 2016] between lucerastat and placebo with corresponding 95% CI. The rejection of the null hypothesis will be solely based on the p-value from the rank analysis of covariance and not the 95% CI of the unadjusted win ratio estimator.

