10.5 Sample size

The planned sample size for this study is 99 subjects using a 2:1 allocation ratio (66 lucerastat, 33 placebo) and is primarily based on a test for the mean difference between lucerastat and placebo in the change from baseline to Month 6 in the “modified” BPI-SF3 score.

The sample size calculation for the primary endpoint analysis is based on the following assumptions: a clinically relevant difference of 2 points on the 11-point scale (0–10) between lucerastat and placebo, a corresponding SD of 3 points, a two-sided type I error of 5%, and equal group variances. These assumptions come from an expected mean decrease from baseline to Month 6 in BPI-SF3 in the lucerastat group of 1.0-1.5 (2-year data for subjects on ERT; [Hoffmann 2007b]), and an expected mean increase from baseline in the placebo group of approximately 0.5 to 1.0 [Weidemann 2014]. Following these assumptions 99 subjects will provide a power of 87.2% to detect a treatment difference between lucerastat and placebo on the primary endpoint. The calculations were conducted using East 6.5 based on a two-sided t-test for independent samples.

For the analysis of the secondary efficacy endpoints, it is expected that about 70% of the randomized subjects will be included in the mFAS-GIS. Under this assumption the assessment of the secondary endpoints may be carried out on about 69 subjects (approximately 46 on lucerastat and 23 on placebo). Little is known from the literature on the expected effect size that might be observed for these endpoints however a reasonable treatment effect on the abdominal pain endpoint (NRS-11) could be a difference (delta) of

1.5–2.5 points on that scale with an expected variability (SD) in the region of 2.5–3.5. For illustration purposes, and in absence of missing data, the power to detect such an effect with this sample size for the analysis of a continuous endpoint is shown in [Table 7](#).

Table 7 Power to detect a treatment difference for continuous secondary endpoints analyzed on the mFAS-GIS for a range of deltas and SDs (n = 69 subjects)

alpha = 5% two-sided			
delta	SD = 2.5	SD = 3.0	SD = 3.5
1.5	63.9%	48.8%	38.0%
2.0	87.0%	73.0%	59.7%
2.5	97.1%	89.5%	78.7%

SD = standard deviation.

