## 2 STUDY DESIGN AND FLOW

This is a prospective, multi-center, double-blind, randomized, placebo-controlled, parallel-group, Phase 3 study.

118 adult subjects with Fabry disease (FD) exhibiting Fabry-associated pain of moderate to severe intensity were randomized in a 2:1 ratio to either lucerastat (approximately 79 subjects) or placebo (approximately 39 subjects).

Treatment allocation was stratified by

- sex
- and
- enzyme replacement therapy (ERT) treatment status at screening
    - “pseudo-naïve” / “treatment naïve” (not treated in last 6 months / never treated)
- vs
- “switch” (subjects treated with ERT at screening).

Once randomized, subjects entered a 6-month, double-blind treatment period. Approximately 36 subjects were included worldwide in a PK profile sub-study.

All English-speaking subjects in the US and Canada were asked to participate in an exit interview sub-study; subjects who accepted performed this interview as soon as possible after the Month 6 or End-of-Treatment (EOT) visit, ideally within 2 weeks.

No interim analysis was planned.

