### **15 EFFICACY ANALYSIS**

#### **15.1 Overall testing strategy**

[figure not shown]
Comparisons of lucerastat vs placebo will be conducted for the primary and secondary endpoints assessed at Month 6.

The Type I error rate will be controlled at a two-sided alpha of 5% for the testing of the four null hypotheses associated with the primary and secondary endpoint comparisons employing a fixed-sequence statistical testing strategy in the following order:

1. Change from baseline to Month 6 in the “modified” BPI-SF3 score of “neuropathic pain at its worst in the last 24 hours”.
2. Change from baseline to Month 6 in plasma Gb3.
3. Change from baseline to Month 6 in the NRS-11 score of “abdominal pain at its worst in the last 24 hours” in subjects with GI symptoms at baseline.
4. Change from baseline to Month 6 in the number of days with at least 1 stool of a BSS consistency Type 6 or 7 in subjects with GI symptoms at baseline.

The order of the fixed-sequence statistical testing strategy is depicted in [Figure 2](#). In the event that the null hypothesis is not rejected for an endpoint in the sequence, claims for statistical significance cannot be made for endpoints that follow in the sequence.

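### Diarrhea days are tested with baseline adjustment but reported with an unadjusted win ratio, so a significant test can come with a 95% CI that includes 1

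*SAP*

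**What the plan says.** SAP 15.1 sets the frame: "The Type I error rate will be controlled at a two-sided alpha of 5% for the testing of the four null hypotheses". Diarrhea days come fourth of the four.

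SAP 15.3.2 tests the endpoint in three steps: fractional midranks of baseline and of change within each sex-by-ERT stratum, a regression of one on the other in each stratum, and a stratified CMH mean score test on the residuals.

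The SAP then says that this test yields no interpretable effect and continues: "Therefore, the magnitude of the treatment effect will be estimated using the unadjusted" win ratio. Protocol 10.3.3.2 says the same: "the magnitude of the treatment effect will be estimated using the unadjusted non-parametric win ratio". The CI comes from a bias-corrected bootstrap on the log win ratio, resampled within treatment arm only.

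Both documents say that rejection depends on the rank-test p-value and, in the SAP's words, "not the 95% CI of the unadjusted win ratio estimator". The summary measure of secondary estimand #3 (protocol Table 3, SAP Table 1) is a win ratio; neither table mentions adjustment or strata.

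**The concern.** This is the only one of the four hypotheses for which test and CI come from different analyses. For neuropathic pain, plasma Gb3 and abdominal pain, both come from one ANCOVA with baseline and the two stratification factors.

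Baseline carries real information here. SAP 4.1.4 admits subjects to the mFAS-GIS on abdominal pain alone, so some will have few or no diarrhea days at baseline and little room to fall. A comparison that ignores baseline discards information that the test uses.

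If the sequence reaches this endpoint and the test succeeds, the report could show a significant p-value beside an interval that includes no effect. Neither document says how to present that. An adjusted estimate chosen after seeing such a result would look post hoc.

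**Working it through.** **The plan's own figures.** Protocol 10.5 says the secondary analyses "may be carried out on about 69 subjects (approximately 46 on lucerastat and 23 on placebo"). For 46/23, a difference of 2 and an SD of 3, the noncentrality is 2/(3 x sqrt(1/46 + 1/23)) = 2.61. Noncentral-t power with 67 degrees of freedom reproduces the stated 73.0%, and all nine cells of Table 7 agree to within 0.1 point. The primary calculation (66/33) gives 87.20% against the stated 87.2%. These figures concern a t-test. Neither document gives power for the rank test or a rate of disagreement between test and CI.

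**Inputs that must be assumed.** Of the GI endpoints the protocol says "Little is known from the literature on the expected effect size that might be observed for these endpoints". The baseline-to-Month 6 correlation is not given, and the distribution is described only as non-normal.

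**Do the ranks yield an effect measure?** In a stratum with n1 lucerastat and n0 placebo subjects, n = n1 + n0, let theta be the probability that lucerastat has the larger decrease, ties counted half. With low ranks for large decreases:
- mean rank, lucerastat = (n1+1)/2 + n0(1 - theta)
- mean rank, placebo = (n0+1)/2 + n1 theta
- difference = n(1/2 - theta)

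Dividing by n+1, as the SAP's fractional ranks do, gives theta = 0.5 - (n+1)/n x rank difference. A baseline-adjusted rank difference therefore gives a baseline-adjusted win probability, and theta/(1 - theta) is the win odds.

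**Why baseline matters.** With equal variances and correlation r between baseline and Month 6, change correlates with baseline at -sqrt((1-r)/2). Linear adjustment leaves a fraction (1+r)/2 of the variance. The SE ratio is sqrt(0.65) = 0.81 at r = 0.3, sqrt(0.75) = 0.87 at 0.5, and sqrt(0.90) = 0.95 at 0.8. This is only a guide for ranks of bounded data, but it shows the gain shrinking as r rises.

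**Simulation of the SAP procedure.** Settings: 46/23, four strata of 30/20/30/20% without stratum effects, no missing data, 800 to 1000 trials per scenario, and a bias-corrected bootstrap with 600 to 1000 resamples. Correlation and shift are on a latent scale.

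| Data | r | Shift (SD) | Test power | Test wins with CI including 1 |
|---|---|---|---|---|
| 0-28 days | 0 | 0.8 | 72% | 41.7% |
| 0-28 days | 0.3 | 0.8 | 78% | 28.6% |
| 0-28 days | 0.5 | 0.6 | 62% | 26.9% |
| 0-28 days | 0.5 | 0.8 | 84% | 18.9% |
| 0-28 days | 0.7 | 0.6 | 75% | 13.7% |
| 0-28 days | 0.85 | 0.4 | 71% | 12.6% |
| normal | 0.5 | 0.6 | 65% | 18.1% |
| normal | 0.5 | 0.8 | 87% | 7.1% |
| normal | 0.85 | 0.4 | 74% | 4.7% |

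- Over all non-null scenarios, at any power, the range was 0-60%.
- The SAP reports that "118 adult subjects with Fabry disease (FD) exhibiting Fabry-associated pain" were randomized. At the planned 70% share that is 118 x 0.70 = 82.6, about 83 subjects (55/28). The range there was 2.6-33%. With 10% missing data at N = 69 it was 10-33%.
- The reverse, a CI excluding 1 beside a non-significant test, occurred in up to about 10% of all trials.
- A stratified test without baseline adjustment disagreed with the same CI in only 4-9% of its wins, so the gap comes mainly from baseline and little from the strata.
- Under the null, the size of the planned test was 3.8-5.9%.

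**Effect of an adjusted companion.** In seven non-null scenarios rerun with a baseline-adjusted, stratified win odds and a bootstrap-based CI, disagreement fell from 9-26% to about 3-6%. Separate runs with test power of 75-84% gave 27% to 7% at r = 0.3, 17% to 5% at 0.5, 15% to 9% at 0.7, and no gain at 0.8 (11% to 12%). A further run, bootstrapping within arm and stratum with 200 resamples, left 10% at r = 0.5; its CI excluded no effect in 5.1-5.5% of null trials.

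**What the code compares.** PROC RANK runs by sex and ERT status and names no new variables, so in `ranks` the variable `chg` already holds within-stratum fractional ranks. The bootstrap reads `data=ranks`. As coded, the win ratio may compare stratum-standardized ranks across strata, whereas the estimand speaks of change from baseline. Simulating that reading gave 21.5% disagreement where the plain reading gave 18.9%.

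**The case against.** The strongest reply is that the choice is open and deliberate. Both documents label the win ratio as unadjusted and keep its CI out of the decision, and the protocol records that the need to change this analysis was discussed with the FDA. An unadjusted win ratio is a legitimate estimator of a marginal estimand, and adjustment mainly buys precision. All of this stands. It is why the win ratio should stay and only a companion is proposed.

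Second, SAP 15.3.2 already plans supportive analyses with adjustment: an MMRM with baseline, sex and ERT status, and a stratified responder analysis. That is partly right. But the MMRM is parametric, on an endpoint moved to ranks because normality was doubted, and the responder analysis covers only subjects with diarrhea at baseline. Neither gives an adjusted version of the win measure.

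Third, win odds count ties as half and a win ratio does not, so substitution would alter the estimand. This is correct, and it argues against replacement.

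A reader might infer that the plan implies a fixed disagreement rate, such as one in five. The documents do not support that: the figure appears near a correlation of 0.5 with fairly high power and moves widely with inputs they do not give. Nor does the mismatch threaten error control, since the CI plays no part in rejection.

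**Conclusion.** The point holds as one of reporting and precision. Test and estimate use different adjustment, and a significant test with a 95% CI including 1 is a realistic outcome: roughly 5-42% of test wins at 60-90% power, for assumed correlations of 0 to 0.85, latent shifts of 0.4 to 0.8 SD, and bounded or normal data. Most of the gap comes from omitting baseline.

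It does not touch type I error or the decision rule, and it matters only if the three earlier hypotheses are rejected. The SAP's reason for having no adjusted effect measure is weak, because the ranks it already computes supply one. That measure reduces disagreement clearly at low to moderate correlation, does not remove it, and may bring nothing at about 0.8. The uncertainty over which values the win ratio compares needs resolving in any case.

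**What to change.** Before unblinding, amend SAP 15.3.2 as follows.

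- Keep the test and the win ratio of secondary estimand #3 unchanged.
- Pre-specify as a companion the baseline-adjusted, stratified win probability and win odds: add arm to the step 2 regression, combine strata with weights n1 x n0/n, and convert with theta = 0.5 - (n+1)/n x adjusted rank difference (lucerastat minus placebo).
- Obtain its 95% CI by repeating these steps in a bootstrap resampled within arm and stratum.
- State whether the win ratio compares overall ranked changes or the within-stratum ranks held in `data=ranks`, and make the code agree.

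The cost is a little programming and a few lines of text, using data already collected. Readers must be told that the two measures treat ties differently. Strata will be small: under the assumed split, a 20% stratum of 69 has about 69 x 0.20 = 13.8 subjects, of whom 13.8/3 = 4.6 are on placebo, so resampling within those cells is coarse.
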